Once participants are invited to the study, they will be sent an email with a link to the Chloe application, which they will download to their mobile device. Chloe will lead them through a detailed description of the study and the informed consent process. At this point, they will also consent to sharing their fitness tracker data, as an option, if they have one. The fitness tracker data will be used to answer sleep questions and other fitness tracker data will be stored for analysis by the FitBiomics team. Once informed consent is obtained, participants will fill out a baseline health and lifestyle survey, where they will also share their mailing address. Once this survey is completed, the participant will be randomized to a high dose Veillonella (15 billion cfu), low dose Veillonella (7.5 billion cfu), or placebo in a 4:4:2 ratio respectively. These capsules will be mailed to the participant during the 2 week baseline period.

Completion of the initial baseline health and habit survey initiates the 2 week baseline period. During this period, participants will fill out daily surveys on sleep, energy, and bowel movements and weekly surveys on other benefits and adverse events (AEs) they have noticed (more details on all surveys can be found in Tables 1 and 2). On the final day of the two week baseline, they will also fill out the Multidimensional Fatigue Inventory (MFI) and General Self-Efficacy (GSE) questionnaires. At this point, participants will begin supplementation. Participants will supplement with one capsule daily for 4 weeks. During the supplementation phase, participants will fill out the same daily and weekly surveys. On the final day of the supplementation period, participants will also fill out the Multidimensional Fatigue Inventory and General Self-Efficacy questionnaires. After supplementation, there will be a two week washout period to monitor patients and to understand the lasting effect of any benefits they experienced. During the washout period, participants will again fill out the same daily and weekly surveys. On the final day of the washout period, there will be two additional surveys: one with some additional questions on changes observed throughout the study and one of open ended questions on the whole study experience.

Figure 1. Study Procedures

[figure not shown]

Table 1. Survey Details

| Survey Name | Survey Details | Number of Questions | Estimated Time to complete | Number of Times Used | Total survey time |

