|---------------------------|---|---------------------|----------------------------|----------------------|-------------------|
| Study sign up form | Form used to express interest in the study, includes questions on participant demographics and to include / exclude participants | 18 | 5 minutes | 1X | 5 minutes |
| Baseline survey | Includes questions on daily habits and lifestyle as well as baseline questions on normal fatigue and energy levels | 31 | 10 minutes | 1X | 10 minutes |
| Daily survey | Daily assessment of the participant's sleep, energy, and bowel movements | 4 | < 1 minute | 56X | 56 minutes |
| Weekly Survey | Participants are asked to look back at their week and report their feelings of fatigue, energy, mood, and health, as well as their exercise and other physical activity | 18 | 5 minutes | 8X | 40 minutes |

| | | | | | |
|----------------------------|---|----|------------|----|-------------|
| MFI | A self-report instrument designed to measure fatigue. It covers the following dimensions: General Fatigue, Physical Fatigue, Mental Fatigue, Reduced Motivation and Reduced Activity. | 20 | 5 minutes | 2X | 10 minutes |
| GSE | PROMIS self-efficacy survey designed to be non-disease specific measure of life management and physical functioning | 4 | < 1 minute | 2 | 2 minutes |
| End of study survey | A repetition of some questions from the baseline survey to assess whether there have been significant changes over the course of the study | 4 | < 1 minute | 1 | 1 minute |
| Experience survey | Mostly open ended questions on experience in the study itself, including questions designed to inform future marketing of Veillonella | 6 | 5 minutes | 1 | 5 minutes |
| Total survey time | | | | | 139 minutes |

Table 2. Survey Schedule

| | Recruitment | Pre-Week 1 | Week 1 | Week 2 | Week 3 | Week 4 | Week 5 | Week 6 | Week 7 | Week 8 |
|----------------------------|-------------|------------|-------------------|-------------------|-------------------|-------------------|-------------------|-------------------|-------------------|-------------------|
| Study sign up form | 1X | | | | | | | | | |
| Informed consent | | 1X | | | | | | | | |
| Baseline survey | | 1X | | | | | | | | |
| Daily survey | | | Daily (7X) |
| Weekly survey | | | 1X at end of week |
| MFI | | | | 1X at end of week | | | | 1X at end of week | | |
| GSE | | | | 1X at end of week | | | | 1X at end of week | | |
| End of study survey | | | | | | | | | | 1X at end of week |

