The publication or presentation of any study results shall comply with all applicable privacy laws, including, but not limited to, the Health Insurance Portability and Accountability Act of 1996. Neither the complete nor any part of the results of the study carried out under this protocol, nor any of the information provided by the sponsor for the purposes of performing the study, will be published or passed on to any third party without the written approval of the Study PI. Any investigator involved with this study is obligated to provide the sponsor with all data derived from the study.

Biostatistical Analysis Plan

Data Source

The source of the data is the results of the questionnaires filled out through the Chloe app as well as the optional fitness tracker data collected over the course of the study.

Analysis Objectives

The goals of this analysis are to identify whether there are statistically significant differences in effects between the placebo and Veillonella groups as well as between the high and low dose Veillonella groups. Furthermore, for any differences that are observed, we would like to understand whether there are any demographic or other participant characteristics that may be associated with benefits or side effects experienced by the participants.

Analysis Sets / Populations / Subgroups

The three groups compared in this study are high dose Veillonella, low dose Veillonella, and placebo.

In addition, we plan to separately analyze results by gender, age, baseline exercise habits, health history, previous probiotic experience, sleep habits, and other lifestyle factors.

For those participants who share fitness tracker data, the fitness tracker data shared through the Chloe app will be analyzed in conjunction with survey data separately from those who did not share fitness tracker data.

Endpoints

The primary endpoints analyzed in this study are:

- Change in reported physical fatigue
- Change in mental / emotional fatigue
- Change in MFI

The secondary endpoints analyzed in this study are:

- Change in reported sleep quality
- Change in frequency of reported physical activity
- Change in intensity of reported physical activity
- Change in reported exercise
- Change in recovery time
- Change in energy level

The exploratory endpoints analyzed in this study are:

- Changes in fitness tracker data
- Change in reported bowel movements
- Change in GSE
- Change in reported mood
- Change in reported digestive health

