- Change in reported general health
- Change in BMI, weight, or waist circumference

Handling of Missing Values

There will likely be missing values related to incomplete or missing surveys. Participants will only be included in the analysis if they completed at least 50% of weekly surveys during each time period: baseline, supplementation, and washout. Values will be binned longitudinally such that each participant included in the analysis has a data point associated with each bin. If there are multiple values associated with a participant in a bin, the mean of those values will be used for the analysis.

Statistical Procedures

The majority of primary and secondary endpoints for this study are questions on the survey which consist of rating scales (generally 1-5 or 1-9). Significant differences between groups for these endpoints will be assessed using an independent T test or Mann-Whitney U test depending on the observed

distribution of the data. For significant changes over time within the same group, a dependent T test will be used.

For differences between groups in terms of primary and secondary endpoints that measure a change in time (e.g. time to recovery in days or hours of sleep), an independent T test or Mann-Whitney U test will be used, depending on the observed distribution of the data. For significant changes over time within the same group, a dependent T test will be used.

To identify demographics associated with any particular response (benefit or side effects), we will use the demographic, health history, and lifestyle information collected in the surveys to build an unsupervised machine learning algorithm (e.g. Random Forest Classifier). If we can build one that effectively classifies the response (AUC > 0.7), we will identify the model's most important features. To confirm that these features are significantly associated with response, we will use an independent T test to assess significant differences between response and non-response.

For all other exploratory endpoints including the optional fitness tracker data, the data type and distribution of that data will determine the statistical analysis used.

Measures to Adjust for Confounders

For all data and endpoints, data can be normalized to the baseline collected values, and change in value at different time points can be compared using the statistical tests described above.

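### The two weekly-survey primary fatigue endpoints have no named deciding time point, so the plan leaves open whether supplementation, washout or either can make them positive

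*Combined protocol and SAP*

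**What the plan says.** The Endpoints section of the Biostatistical Analysis Plan lists three primary endpoints. Two are given as "Change in reported physical fatigue" and "Change in mental / emotional fatigue", with no week, period or summary measure. The third is the change in MFI.

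The plan does not name the instrument for the first two. Table 1 describes the weekly survey as the repeated one that asks about fatigue: "Participants are asked to look back at their week and report their feelings of fatigue, energy, mood, and health". Its row in that table reads "18 | 5 minutes | 8X | 40 minutes", so it is given eight times. Table 2 places these at the ends of Weeks 1 to 8. Under Details Study Procedures, baseline lasts two weeks, then "Participants will supplement with one capsule daily for 4 weeks", then there are two weeks of washout, for which the text says: "During the washout period, participants will again fill out the same daily and weekly surveys".

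Under Measures to Adjust for Confounders the plan says that values for all data and endpoints may be normalized to baseline and that "change in value at different time points can be compared using the statistical tests described above". The tests meant are those under Statistical Procedures: independent t or Mann-Whitney between groups. No significance level, multiplicity rule or repeated-measures model is stated.

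Handling of Missing Values requires at least half of the weekly surveys in each of the three periods. It says that values are binned over time, that every analysed participant has a value in every bin, and that multiple values in a bin are averaged. Bin width is not given.

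**The concern.** Each of these two endpoints has six post-baseline weekly values, four while capsules are taken and two afterwards. The periods answer different questions: whether fatigue differs during use, and whether any difference lasts after use stops. If neither is named as deciding, the choice can be made after the data are seen.

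Two things are at stake. First, more than one chance at a positive result per endpoint raises the false-positive rate before arms or endpoints are counted. Second, the plan has no rule for a case where the periods differ. A washout-only difference could be reported as a positive primary result, or a washout null could be set against an effect seen during supplementation.

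**Working it through.** The plan states no error rate, so there is no figure to reproduce. The check asks what the wording allows.

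**Inputs from the documents**
- Baseline: 2 weekly values (Weeks 1-2).
- Supplementation: 4 weekly values (Weeks 3-6).
- Washout: 2 weekly values (Weeks 7-8).
- Separate between-group tests, no adjustment.

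**Assumptions, not in the documents**
- Two-sided 0.05 per test.
- One pairwise arm contrast, one endpoint.
- Any significant time point counts as success.
- Weekly scores with variance 1 and constant week-to-week correlation r (relaxed below).

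**Step 1: correlation of the two period changes.** For a post-baseline mean of m weeks and a baseline mean of 2 weeks:
- Variance of change = (1 - r)(1/2 + 1/m).
- Supplementation (m = 4): 0.75(1 - r). Washout (m = 2): 1.00(1 - r).
- Covariance, from the shared baseline: 0.50(1 - r).
- Correlation = 0.50 / √(0.75 × 1.00) = 0.577, whatever r is. At r = 0.5 the three terms are 0.375, 0.50 and 0.25.

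**Step 2: two period tests.**
- Either direction: 1 - Pr(|Z1| ≤ 1.96 and |Z2| ≤ 1.96) at correlation 0.577 = 8.8%.
- Favourable direction only: 1 - Pr(Z1 ≤ 1.96 and Z2 ≤ 1.96) = 4.4%, against 2.5% for one test.

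**Step 3: six weekly tests, if bins were weekly.** The variance of a single-week change is 1.50(1 - r), so the correlation is 0.50/1.50 = 0.333. Any of six, either direction: 23.6%. Favourable direction only: 11.9%.

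**Step 4: other correlations.**

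| Structure | Two periods | Six weeks |
|---|---|---|
| Independent tests | 9.75% | 26.5% |
| Change from baseline, constant correlation | 8.8% | 23.6% |
| Change from baseline, AR(1) 0.3 to 0.9 | 8.1-8.8% | 16.0-21.5% |
| Test statistics all correlated 0.9 | 7.0% | 10.8% |

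Every entry exceeds 5%. The first row is an upper bound that a shared baseline rules out in practice.

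**Step 5: which row of bins fits the plan?** Half of four supplementation surveys is two, and half of two washout surveys is one. A participant who just qualifies may therefore have 2 + 1 = 3 of 6 post-baseline weekly values. Weekly bins would then be empty for that participant, although the plan says that every analysed participant has a value in each bin. Of these two, only period-wide bins are filled by the 50% rule. The two-period column is the better reading; the six-week column is a conditional worst case.

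**Step 6: the MFI.** The schedule fixes its time point: end of Week 2, and then "On the final day of the supplementation period, participants will also fill out the Multidimensional Fatigue Inventory and General Self-Efficacy questionnaires". It is not given in washout, so the point does not apply to it.

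**The case against.** The strongest reply is that the role of washout is not blank. Details Study Procedures says it serves to monitor participants and to see whether benefits last, which presupposes an earlier benefit. The MFI, the third primary endpoint, stops at the end of supplementation. Both point to supplementation as the main period. This stands as evidence of intent and makes the gap smaller. It is not an analysis rule, however: the analysis plan never ranks the periods, and it requires half of the washout surveys before a participant is analysed at all.

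A second reply is that the sentence on different time points is permissive and sits in a section about baseline normalization. That also stands. The inflation is what the wording allows, not a property of a stated test.

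A reader might go further and infer that each endpoint simply has a false-positive rate of 9-24%. The documents do not support that: they give no alpha, they do not say that any significant time point wins, and the top of that range needs weekly bins. A reader might also infer that the two periods would contradict each other. A difference in one period and not in the other may only be an effect that fades, which washout is meant to show. Finally, one might claim a loss of power from mixing the periods. That cannot be sized, because the plan gives no analysed sample size or effect size and proposes no average over all six weeks.

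**Conclusion.** The point holds as a missing decision rule. For two of the three primary endpoints the plan names no deciding time point, permits comparisons at several, and does not place washout below supplementation. This much rests on the text alone.

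The size is conditional on the assumptions listed above. With period bins, about 8-9% per endpoint and contrast instead of 5%, or 4.4% instead of 2.5% in the favourable direction. With weekly bins, about 11-24% depending on correlation. The three arm comparisons and the number of primary endpoints are not counted in these figures. It should be corrected before analysis, but nothing in the design or data collection is compromised.

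**What to change.** In Endpoints, state that for reported physical fatigue and mental/emotional fatigue the primary comparison is the change from the baseline period (Weeks 1-2) to the supplementation period (Weeks 3-6), with one value per participant. A single end-of-supplementation value, matching the MFI, would also serve if it is fixed in advance.

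State that changes at single weeks and in washout (Weeks 7-8) are supportive, are reported with 95% confidence intervals, and cannot make a primary endpoint positive. Under Measures to Adjust for Confounders, limit the permission to compare different time points to these supportive analyses.

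This brings each endpoint back to one test per arm contrast, 5% at the assumed level. It needs SAP wording only and no new data. The small downside is that a difference seen only in one week or only in washout can no longer be claimed as a primary result.

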In addition, there is a question included in the weekly surveys assessing how participants are generally feeling about their life, which they respond to using a rating scale from 1 (pessimistic) to 9 (optimistic). If necessary, we can normalize the weekly survey data using this rating to confirm that participant life and stress outside the study are not affecting how they respond to the surveys.

QC Plans

All analyses will be performed by a study bioinformatician or data scientist. All code used for the analysis will be saved using version control software such as Git in the format of Python notebooks. These notebooks will be reviewed by other study staff for errors and certified that analyses are correct prior to any written or oral reports, presentations, or publications on the results of the study.

Programming Plans

All code for these analyses will be written using Python 3 in Jupyter notebooks. The pandas library will be used for importing the data, manipulating it in a data frame, and exporting it as excel or comma-separated files. The Numpy and Scipy libraries will be used for all statistical analysis and the Sci-Kit Learn library will be used for machine learning analyses. Matplotlib and Seaborn libraries will be used for visualization of the data as graphs and charts.

Investigator Conflict of Interest

Investigators will disclose any conflict of interest.

Any investigator who has a conflict of interest with this study (patent ownership, royalties, or financial gain greater than the minimum allowable by their institution, etc.) must have the conflict reviewed by a properly constituted Conflict of Interest Committee with a Committee-sanctioned conflict management

plan that has been reviewed and approved by the study Sponsor prior to participation in this study. All investigators will follow the conflict of interest policy.

References

3. Gross K, Santiago M, Krieger JM, Hagele AM, Zielinska K, Scheiman J, et al. *Acute Impact of Veillonella atypica FB0054 Supplementation on Exercise Performance and Lactate Changes: A Randomized, Crossover Pilot.* *Nutrients. In Review.*

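### Between-arm tests on change scores leave baseline precision unused, and an undefined outlook normalisation could distort two fatigue endpoints if it is used to compare arms

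*Combined protocol and SAP*

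**What the plan says.** All analysis text is in the Biostatistical Analysis Plan of the combined protocol and SAP.

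- **Test.** Under Statistical Procedures, group differences on the rating-scale endpoints "will be assessed using an independent T test or Mann-Whitney U test", chosen by the observed distribution.
- **Baseline.** Under Measures to Adjust for Confounders, "data can be normalized to the baseline collected values, and change in value at different time points can be compared" with those same tests. The wording is permissive, and no model with baseline as a covariate appears.
- **Outlook rating.** The same section describes a weekly item on how participants feel about their life, from 1 (pessimistic) to 9 (optimistic), and adds: "If necessary, we can normalize the weekly survey data using this rating". The purpose given is "to confirm that participant life and stress outside the study are not affecting how they respond to the surveys".
- **Timing.** Details Study Procedures and Table 2 repeat the weekly survey in all eight weeks: baseline in Weeks 1-2, supplementation in Weeks 3-6, washout in Weeks 7-8. The MFI is given at the end of Weeks 2 and 6 only.
- **Endpoints.** The three primaries are change in reported physical fatigue, in mental/emotional fatigue, and in MFI. Table 1 places fatigue questions in the weekly survey, so the normalisation appears to reach the first two. The MFI is a separate instrument.
- **Repeated values.** Under Handling of Missing Values, where a participant has several values in a bin, "the mean of those values will be used for the analysis". The bins are not defined.

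**The concern.** **Precision.** A change score subtracts the whole baseline value. Unless baseline and follow-up correlate perfectly, that is more than the optimal amount, and the excess adds noise. The baseline values are already collected, so the loss is avoidable. It weighs most on comparisons with placebo, the smallest arm under 4:4:2 allocation.

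**Bias, conditional.** From Week 3 on, the outlook rating is itself open to treatment. The plan gives grounds for thinking it might move: mood is an exploratory endpoint, and Risk/Safety Information lists nervousness and anxiety as very common with the product. Dividing fatigue by such a rating, or regressing on it, can transfer an effect on outlook into the fatigue comparison. Randomisation already balances outside stress in expectation, so the between-arm comparison does not need this step. With no trigger fixed, the decision to use it could follow sight of the results.

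**Working it through.** The documents give no power, SD, correlation or effect size, so there is no figure of the plan's to reproduce.

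**Inputs from the documents.** Allocation is 4:4:2 (Details Study Procedures). Up to 1,000 invitees are estimated (Recruitment). If all were randomised and analysed, that is 1,000 × 0.4 = 400 per dose and 1,000 × 0.2 = 200 on placebo, which is an upper bound.

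**1. Precision (closed form)**

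Assume unit variance and equal correlation r between any two weeks. Average b baseline weeks and f follow-up weeks:

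- vb = (1 + (b−1)r)/b and vf = (1 + (f−1)r)/f
- variance of change = vb + vf − 2r
- variance under ANCOVA = vf − r²/vb

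The extra sample needed by change scores is the ratio of the two variances minus 1.

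| Outcome | r | Change | ANCOVA | Extra participants |
|---|---|---|---|---|
| MFI (b=1, f=1) | 0.3 | 1.400 | 0.910 | 54% |
| | 0.5 | 1.000 | 0.750 | 33% |
| | 0.7 | 0.600 | 0.510 | 18% |
| Weekly item, 2-week v 4-week means | 0.3 | 0.525 | 0.337 | 56% |
| | 0.5 | 0.375 | 0.292 | 29% |
| | 0.7 | 0.225 | 0.199 | 13% |

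The difference detectable with 80% power at two-sided 5% is 2.802 × √(variance × (1/400 + 1/200)), where 2.802 = 1.960 + 0.842. For the MFI at r = 0.5:

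- change: 2.802 × √(1.000 × 0.0075) = 0.243 SD
- ANCOVA: 2.802 × √(0.750 × 0.0075) = 0.210 SD

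**2. Normalisation (simulation, all inputs assumed)**

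Fatigue item 1-5, mean 3, SD 1. Outlook 1-9, mean 6, SD 1.5. Week-to-week correlation 0.5. Item-rating correlation 0 to −0.4 if a higher score means more fatigue, or 0 to +0.4 if it means less. Scores are rounded and truncated; 400 v 200; one baseline and one follow-up week; no common time trend; no true fatigue effect. The table shows how often each analysis rejects at 5%.

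| Analysis | Rating shift +0.3 | Rating shift +0.5 |
|---|---|---|
| Plain change, or baseline ANCOVA | 4-6% | 4-6% |
| Change in fatigue/outlook ratio | about 17-31% | about 40-67% |
| Change regressed on change in rating, correlation ±0.4 | about 13% | about 26-27% |
| Same regression, correlation 0 | about 5% | about 5% |
| Change divided by the rating | about 5% | about 5% |

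A rising rating lowers the ratio. That reads as benefit if higher scores mean more fatigue, and as harm if they mean less. The plan does not state how the items are scored.

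An effect can also be hidden. Take a true 0.25-point improvement, higher = more fatigue, and a rating shift of −0.3. The change in ratio then rejects in about 5-6% of trials. With no shift it rejects in about 30-41%, against 74-76% for the t test on change.

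**Sensitivity.** Add an equal 0.5 to 1-point fall in fatigue in both arms (shift +0.5, higher = more fatigue). Change in ratio falls to about 26-41%, and change divided by rating rises from about 5% to about 7-15%.

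**The case against.** **The normalisation may be only a check.** The text is permissive and gives a purpose that reads as confirming a result already obtained by the planned tests. This stands in part. A reader might infer that the plan will bias its primary comparison, or that no role at all is given. The documents support neither. Bias requires that the option is used, that its result is used to compare arms, that treatment moves outlook, and that the formula is a vulnerable one. The documents do not show that treatment moves outlook, or in which direction. What remains is that nothing confines the result to a check.

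**The simulated sizes are not robust.** This stands. Every input is assumed, the 1-9 item format that the plan also allows was not used for these figures, and a common time trend shifts them. They show that the problem can be large, not how large it would be.

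**A test on change is valid and common, so ANCOVA is a preference.** The premise is right, and the plan states no power figure that the choice breaks. A reader might infer that the change score is biased; relative to ANCOVA it is only less precise. The gain is still available on all three primaries at almost no cost.

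**Baseline follows randomisation.** Details Study Procedures randomises before Week 1 and mails capsules during the baseline period. The caution is fair, but the change score relies on the same values. Likewise, the rule requiring "at least 50% of weekly surveys during each time period" selects participants partly on post-treatment behaviour under either method, and ANCOVA does not cure that.

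**No new software is needed.** Correct. Under Programming Plans, "The Numpy and Scipy libraries will be used for all statistical analysis", and Numpy can fit this model.

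**Conclusion.** The concern holds as two points of different standing.

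1. **Precision, the main point.** Change scores are less efficient than adjusting for the pre-supplementation value. The MFI needs 54%, 33% or 18% more participants, and two-week v four-week means of weekly items 56%, 29% or 13% more, at assumed correlations of 0.3, 0.5 or 0.7. No bias follows from this.
2. **Bias, conditional.** Formula, trigger and analysis status are missing for an adjustment that uses on-treatment ratings and appears to reach two of the three primaries. If it is used to compare arms and treatment moves outlook, a ratio can create or hide a fatigue effect. So can a regression on the rating when fatigue and outlook are correlated. The MFI is not exposed, and the simulated rates hold only for the stated assumptions.

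The plan should be changed before outcomes are viewed by arm. Confidence is medium, because the sizes rest on inputs that the documents do not give.

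**What to change.** **(a) Baseline adjustment.** Make the between-arm analysis of the primary endpoints, and of secondary endpoints on the same scales, an ANCOVA with robust standard errors.

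- Outcome: the mean of available Week 3-6 values (Week 6 for MFI), or another window fixed before outcomes are viewed by arm.
- Covariates: arm, and the pre-supplementation value of the same outcome (mean of available Week 1-2 values; Week 2 for MFI).
- Keep the planned t or Mann-Whitney test on change as a sensitivity analysis.
- State that Week 1-2 values are collected after randomisation but before supplementation. The analysis therefore relies, as the change score does, on participants not starting capsules early and not knowing their arm.

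**(b) Outlook rating.** Replace the normalisation sentence under Measures to Adjust for Confounders with, for example: *Primary between-arm comparisons use no outlook rating collected from Week 3 on. If outlook is adjusted for, only the Week 1-2 mean is used, as a covariate. Any analysis using later ratings is a labelled exploratory sensitivity analysis, with its formula fixed before outcomes are viewed by arm.*

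**Cost.** Minor wording and a few lines of code, with no new data. A regression library would be convenient but is not required. The downsides are a linear model on short ordinal items, which is why the planned test is kept, and a precision gain that shrinks as the baseline correlation rises.
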